2. OVERVIEW OF STUDY DESIGN

This is a retrospective study of prospectively collected patient data with the use of secondary patient data from both paper and electronic patient files. All patients are treatment naïve at time of diagnosis. Both migalastat and ERT will be studied retrospectively. Also untreated patients will be studied by assessment of relevant clinical and laboratory variables. The analysis will originate at the time of diagnosis.

The patients have been followed for more than 20 years from 2001 until December 2023. All identified patients with Fabry disease, whether receiving specific Fabry medication or not, have been offered annual or biannual thorough workups including examinations of Fabry associated organ function and symptoms. The study will be carried out at the Danish National Fabry Centre, Department of Endocrinology, Copenhagen University Hospital.

All patients from the Danish National Fabry Centre will be included. Subgrouping is aimed at depending on available numbers: non-amenable, amenable, classic, non-classic, males, females, treated including type of treatment or untreated.

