6. HANDLING OF DROPOUTS AND MISSING VALUES

6.1. Imputation of Dates

SAEs and FACEs

If onset date is completely missing, then the onset date is set to the date of enrollment unless end date is before the date of enrollment, in which case the onset date is set to 28 days prior to end date.

If (year is present and month and day are missing) or (year and day are present and month is missing):

- If year = year of enrollment, then set month and day to month and day of enrollment unless end date is before the date of enrollment, in which case the onset date is set to 28 days prior to end date.
- If year < year of enrollment, then set month and day to 31 December.
- If year > year of enrollment, then the following applies:
 - If year = year of first treatment switch, then set month and day to month and day of first treatment switch unless end date is before the date of treatment switch, in which case the onset date is set to 28 days prior to end date.
 - If there is no treatment switch, then set month and day to 1 January.

If month and year are present and day is missing:

- If year = year of enrollment and if month = month of enrollment, then set day to day of enrollment date unless end date is before the date of enrollment, in which case the onset date is set to 28 days prior to end date.
- If month < month of enrollment, then set day to last day of the month.
- If month > month of enrollment, then the following applies:
 - If year = year of first treatment switch and if month = month of first treatment switch, then set the day to the day of treatment switch unless end date is before the date of treatment switch, in which case the onset date is set to 28 days prior to end date.
 - If there is no treatment switch, then set day to first day of the month.

For all other cases, set onset date to the date of enrollment unless end date is before the date of enrollment, in which case the onset date is set to 28 days prior to end date.

End date will not be imputed.

Start and End of Therapy Prior to Study Enrollment

The following dates are essential for analysis: the end date of Fabry disease therapy prior to enrollment and the start date of ongoing Fabry therapy for the migalastat-treated patients and for the ERT-treated patients. These dates will be used to determine treatment duration prior to enrollment.

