Prior to imputation of dates, the percentage of patients with completely missing start of therapy date, and separately with missing month will be calculated and presented in a table overall and by treatment group at enrollment.

Similarly, the percentage of patients with completely missing end of therapy date, and separately with missing month will be calculated and presented in a table overall and by treatment group at enrollment.

At least the year needs to be present to determine if the patients are eligible for inclusion in the Primary and Secondary Effectiveness Populations.

The following rules apply to the start date:

- If year is present and month and day are missing: set month and day to 1 July.
- If year and day are present and month is missing: set month to July.
- If year and month are present and day is missing: set day to the 15th of the month.

The following rules apply to the end date:

- If the end date is completely missing and the patient did not switch therapy, then the end date is imputed as the discontinuation date.
- If the end date is completely missing and the patient switched therapy, then the end date is imputed as the therapy switch date.
- If year is present and different from the year of the start date, and month and day are missing: set month and day to 1 July.
- If year is present and the same as the year of the start date, and month and day are missing: set month and day to 31 December.
- If year and day are present and month is missing: set month to July.
- If year and month are present and day is missing: set day to the 15th of the month.

Any partial dates will be displayed in data listings without and with imputation of missing days and/or months.

Treatment Switch

Prior to imputation of dates, the percentage of patients with completely missing switch of therapy date, and separately, the percentage of patients with missing month will be calculated and presented in a single table overall, and by treatment group at enrollment. Patients can change therapy more than once during the 20-year period. The percentages of patients with any completely missing switch of therapy dates or any missing therapy switch month will be presented. Additionally, a table with percentages of missing switch dates by group a patient switched to (migalastat-treated, ERT, untreated) will be presented.

The following rules apply to start date of new or switched therapy:

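### SAP 6.1 places a partly dated FACE from the period of the first treatment switch on the switch date, so some earlier events cross the boundary between the treatment periods being compared

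*SAP*

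**What the plan says.** SAP 6.1 gives one set of onset-date rules for SAEs and FACEs together.

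- **Year only, in a year after enrollment:** "If year = year of first treatment switch, then set month and day to month and day of first treatment switch".
- **Month and year known, month later than the enrollment month:** the switch day is used if the year matches and "month = month of first treatment switch, then set the day to the day of treatment switch".
- **Exception to both:** "unless end date is before the date of treatment switch". Onset then goes 28 days ahead of that end date. The section adds "End date will not be imputed", so the exception needs an end date that was actually recorded.
- **Enrollment year:** a year-only event is caught earlier in the list by "If year = year of enrollment, then set month and day to month and day of enrollment".

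Other sections decide which therapy receives the event.

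- SAP 2: "All patients are treatment naïve at time of diagnosis". SAP 5.1 and 5.2.1 use the word switch for going from untreated to a drug, but no section defines *first treatment switch*.
- SAP 13.1.1, primary analysis: a treated patient's events count until 30 days after stopping or switching. An untreated patient's window closes when therapy starts, with no carry-over. Previous FACE, a covariate, is judged at the Analysis Start Date.
- SAP 11.2: the clock starts at treatment start for migalastat versus ERT, and at diagnosis for migalastat versus untreated.
- SAP 13.1.1 (per-period times) and 13.3 (incidence): the window for a new therapy opens on the switch date.
- Protocol, event tables under Registration of treatment: each FACE has a date of event and a yes/no field. No end date is shown.

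**The concern.** Charging an undated event to the newer treatment is a cautious convention for safety reporting. FACEs, however, are the primary effectiveness endpoint, and there the same convention moves outcome events between the groups being compared, always from the earlier period to the later one.

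The events most exposed are those that led to a change of treatment, because they cluster shortly before the switch. An event that prompted a patient to start a drug would be recorded as happening on that drug. The untreated experience would then look better than it was and the on-drug experience worse. In an analysis that starts at treatment start, the patient would also lose the flag for a previous FACE.

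**Working it through.** The documents give no event count, power calculation or share of partial dates, so there is no plan figure to reproduce. The check has four steps.

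**1. The rule applied literally.** Take enrollment on 15 June 2008 and a first switch on 2 October 2017 (invented dates).

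- A FACE on 10 March 2017 recorded as 2017 is set to 2 October 2017, 206 days late. With a recorded end date of 20 March 2017, it is set to 20 February 2017.
- With the switch on 28 October 2017, a FACE recorded as October 2017 is set to 28 October. Had enrollment been in a November, the month rule would give 31 October. Had it been in an October of an earlier year, the event would fall to the catch-all and go to the enrollment date.

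**2. Share of events that truly preceded the switch.** Assume event day and switch day are independent and uniform over a period of *n* days. Then P(event strictly before switch) = (n − 1)/(2n), and the mean delay among those events is (n + 1)/3 days.

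| Date known | n | Share before switch | Mean delay of those events |
|---|---|---|---|
| Year only | 365 | 364/730 = 49.9% | 366/3 = 122 days |
| Month and year | 30 | 29/60 = 48.3% | 31/3 = 10.3 days |
| Month and year | 31 | 30/62 = 48.4% | 32/3 = 10.7 days |

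For a given switch date in the year, the share is 31/365 = 8% on 1 February, 181/365 = 50% on 1 July and 334/365 = 92% on 1 December. If the hazard before a mid-year switch is *k* times that after it, the share is k/(k + 1): 67% for k = 2, 75% for k = 3, 83% for k = 5. The SAP rule places 0% before the switch unless an earlier end date is on file.

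The events that truly followed the switch keep the right therapy, but their onset is also pulled back to the switch date.

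**3. Where the moved event lands.**

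| Analysis | Event imputed to the switch date |
|---|---|
| Primary, untreated patient starting therapy | On the edge of the untreated window; no same-day rule |
| Migalastat versus ERT, first switch = treatment start | First day on drug; by the SAP 7.2 formula day 1, or 1/30.4 = 0.033 months; no longer a previous FACE |
| Primary, drug-to-drug switch | Stays with the old drug (30-day carry-over) |
| Per-period times and incidence | New therapy; with the 30-day carry-over it can also count for the old drug |

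**4. Size under assumed inputs.** A simulation isolated the year-only rule. All inputs except the 115 patients are assumptions:

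- 115 patients, all going from untreated to therapy;
- 8 years before the switch and 5 years after;
- a FACE rate of 0.02 or 0.04 per year, with the on-therapy rate equal to the baseline untreated rate;
- hazard multiplied by 1 or 3 in the six months before the switch;
- moved events credited to the new therapy.

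Rate ratio = (first FACEs ÷ years on therapy) ÷ (first FACEs ÷ years untreated). Ranges span the two event rates.

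| Hazard before switch | Year-only share | Events moved per study | Ratio, true dates | Ratio, SAP rule |
|---|---|---|---|---|
| ×1 | 10% | 0.10–0.17 | 1.00 | 1.01–1.02 |
| ×1 | 30% | 0.30–0.50 | 1.00–1.01 | 1.04–1.05 |
| ×1 | 50% | 0.50–0.84 | 1.00 | 1.07–1.08 |
| ×3 | 10% | 0.24–0.42 | 0.90–0.91 | 0.93–0.94 |
| ×3 | 30% | 0.72–1.25 | 0.89–0.91 | 0.99–1.00 |
| ×3 | 50% | 1.19–2.07 | 0.90 | 1.06–1.07 |

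Hand check at rate 0.02, ×1: untreated time in the switch year averages half a year, and exp(−0.02 × 7.5) = 0.86 of patients are still event-free. So 115 × 0.5 × 0.02 × 0.86 = 0.99 events are exposed, of which 10% is 0.10 and 50% is 0.49, in line with the table. In the ×3 rows the ratio near 0.90 reflects the raised untreated rate, not a drug effect.

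**The case against.** Several stronger readings are tempting, and the documents do not support them.

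- **Every such event is charged to the new therapy and removed from the old one.** This is not so in the primary analysis for a drug-to-drug switch, where the carry-over keeps the event with the old drug. SAP 3.1 also limits the formal analysis to the initial treatment cohort.
- **Events pile up at time zero in the primary comparison.** SAP 11.2 starts migalastat versus untreated at diagnosis, so a switch-date event is not at the origin there. SAP 3.1 says treatment start for treated patients, so the two sections disagree. The first-day problem belongs to migalastat versus ERT and the per-period times.
- **SAP 6.1 contradicts itself because it uses mid-points elsewhere.** The rule "If year is present and month and day are missing: set month and day to 1 July" is for therapy before enrollment. For therapy started or switched during the study, the section uses visit dates, the first or last day of the month, or the day before the next switch.
- **The on-drug count is inflated by 10% to 45%.** Assuming 5 true on-drug events and 1 to 3 partly dated ones, 50% to 75% of which truly came before the switch, gives 0.5/5 to 2.25/5. None of these inputs is in the documents.

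Two further objections carry weight. The missing end date is read from the protocol's tables, labelled V1; the SAP cites version 2 and an eCRF that is not in the documents. The protocol also expects events to be registered at their specific date, so partial dates may be few.

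These points narrow the scope and leave the size open. They do not change what the rule does at starts from untreated, in migalastat versus ERT, or in the per-period and incidence analyses.

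**Conclusion.** The concern holds in this limited form. SAP 6.1 moves partly dated FACEs onto the first switch date whatever their true timing. Under uniform timing, about half of those it reaches came from the earlier period, and more if events prompt switches. The year-only rule does not reach the enrollment year, and the month rule works only for months later than the enrollment month.

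Much depends on *first treatment switch*. If it includes the first start of a drug, the rule acts at the untreated-to-treated boundary and at the time origin of migalastat versus ERT. If it does not, only later changes are affected and the problem is smaller.

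The size cannot be fixed from the documents. SAP 6.1 tabulates missing therapy dates but not missing FACE dates. The simulated shifts are illustrations, probably small if few dates are partial. They are unadjusted rate ratios for untreated versus therapy. For migalastat versus ERT even the direction is open, because both drugs receive moved events and the net effect depends on which has more partly dated FACEs around its start. The rule is worth changing before FACE data are analysed, because no planned sensitivity analysis would reveal its effect.

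**What to change.** 1. For the FACE effectiveness analyses, replace the switch-date rule with a neutral one: the mid-point of, or uniform draws over, the interval compatible with known dates such as enrollment, visits and death. A mid-point is simpler, but for any one switch date it always falls on the same side; uniform draws avoid that.
2. Define *first treatment switch*, stating whether the first start of a drug counts, and state which therapy owns an event dated on the switch day.
3. Tabulate partial FACE dates (year only, month only), overall and by treatment group.
4. Rerun the primary and incidence analyses with all such events placed before the switch, and again with all placed after it.
5. Where a FACE is also an SAE, use the same onset date in both analyses, so that one event is not assigned to two therapies.

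The cost is SAP wording, one table and short sensitivity runs. No new data are needed.

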3. STUDY ENDPOINTS

3.1. Primary Effectiveness Analysis

The primary endpoint is time to first FACE (cardiac, renal, or cerebrovascular events) ") since start of treatment for migalastat and or ERT and from time of diagnosis for untreated with particular focus on the added value of the recent addition of migalastat as a treatment option. A formal statistical analysis will be using the initial treatment cohort. Descriptive statistics will be calculated since each start of treatment (after each switch).

FACEs are defined as the following:

- Cardiac clinical events:
 - Myocardial infarction
 - New symptomatic arrhythmia requiring medication, direct current cardioversion, or interventional procedure (e.g., ablation, pacemaker, or defibrillator implantation)
 - Unstable angina defined by national practice guidelines and accompanied by electrocardiographic changes and non-ST segment elevation myocardial infarction [UA/NSTEMI]) and accompanied by electrocardiographic changes
 - Congestive heart failure requiring hospitalization
 - Any major cardiac medical procedure (e.g., valve replacement, stent-implantation, transplant, or persistent atrial fibrillation)
- Cerebrovascular clinical events:
 - Stroke (documented by a physician)
 - Transient ischemic attack (documented by a physician)
- Renal clinical events
 - Doubling of serum creatinine level from the start of analysis (2 consecutive values)
 - End-stage renal disease (ESRD) requiring long-term dialysis or transplantation
- Death due to FACEs

All FACEs will be analyzed together as a composite and separately in each category (cardiac, cerebrovascular, and renal). Death due to FACE will be analyzed under the category in which it occurred (cardiac, cerebrovascular, or renal).

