11. DEFINITION OF STUDY TIME POINTS

11.1. Definition of Diagnosis Date

Enrollment is the date on which the patient was diagnosed with the Fabry disease. For analysis of assessments which were not collected on the diagnosis date, the assessment closest to the diagnosis date will be utilized. If there are 2 assessments that are equidistant from the diagnosis date, then the assessment prior to diagnosis will be utilized.

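### SAP 6.1 has no rule for some partly dated FACEs and SAEs when the first treatment switch fell in another year or month; read literally, its catch-all moves the onset back to diagnosis

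*SAP*

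**What the plan says.** SAP 6.1 (Imputation of Dates, SAEs and FACEs) sets out blocks by how much of the onset date is known.

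- **Year known, month missing, year after enrollment.** There are two sub-rules. One is "If year = year of first treatment switch, then set month and day to month and day of first treatment switch"; the other is "If there is no treatment switch, then set month and day to 1 January".
- **Month and year known, day missing.** If both match enrollment, the enrollment day is used. Otherwise the test is on the calendar month: "If month < month of enrollment, then set day to last day of the month", or "If month > month of enrollment, then the following applies". What follows the second test is the same pair: the year and month equal those of the first switch, or there is no switch (first of the month).
- **Catch-all.** "For all other cases, set onset date to the date of enrollment unless end date is before the date of enrollment"; in that exception the onset is counted back 28 days from the end date.

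SAP 11.1 fixes the meaning of enrollment: "Enrollment is the date on which the patient was diagnosed with the Fabry disease". SAP 6.2 only refers back to 6.1, and no other section supplies a rule.

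The imputed date feeds the primary endpoint. SAP 3.1 measures time to first FACE "since start of treatment for migalastat and or ERT and from time of diagnosis for untreated" and adds: "A formal statistical analysis will be using the initial treatment cohort". SAP 11.2 instead starts the clock at diagnosis for migalastat against untreated.

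**The concern.** The two sub-rules in each block leave out a third case: the patient did switch, but in a different year or month from the event. SAP 6.1 itself notes that patients may change therapy more than once over the 20 years, so this case is to be expected. The next applicable text is the catch-all, which discards a year that is known. Its exception, an end date before enrollment, cannot apply to an event after enrollment.

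Because the gap depends on having switched, the misdating is tied to the exposure being compared. SAP 13.1.1 decides whether a FACE counts by where it falls relative to the Analysis Start Date and to therapy changes, so a reset onset can alter that decision:

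- In an initially untreated patient, a FACE after therapy start, which 13.1.1 excludes, can become an untreated event at time zero.
- On a treatment-start clock, a FACE on migalastat can fall before the Analysis Start Date and become previous history, which is a model covariate.
- On a diagnosis clock, for a patient put on migalastat within 3 months of enrollment who later switches, a post-switch FACE that 13.1.1 excludes can count against migalastat at time zero.

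**Working it through.** The SAP gives no figure to reproduce; the check is to follow the rules as written.

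**Example (assumed patient, no end date recorded).** Diagnosed 10 March 2005, ERT from 1 February 2006, migalastat from 15 June 2017. Results are the same whether the first switch is taken as 2006 or 2017.

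| Recorded onset | Literal reading | Catch-all belongs only to the month-year block | No switch read as none in that period | Never-switcher, literal |
|---|---|---|---|---|
| 2019 | 10 Mar 2005 | no rule | 1 Jan 2019 | 1 Jan 2019 |
| May 2019 | 10 Mar 2005 | 10 Mar 2005 | 1 May 2019 | 1 May 2019 |
| Mar 2019 | 10 Mar 2005 | 10 Mar 2005 | 10 Mar 2005 | 10 Mar 2005 |
| Feb 2019 | 28 Feb 2019 | 28 Feb 2019 | 28 Feb 2019 | 28 Feb 2019 |

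Displacement of 2019, in years: from 10 March 2005 to 1 January 2019 is 5,045 days / 365.25 = 13.8; to 31 December 2019 it is 5,409 / 365.25 = 14.8.

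The March row is a separate fault. The month tests carry no year, so an event in the enrollment calendar month of a later year is neither earlier nor later than enrollment, and goes to the catch-all. The February row marks the boundary: an earlier calendar month is caught first by the last-day rule and keeps its recorded month. The missing year also works backwards. A pre-diagnosis FACE recorded as May 2003 in this patient passes the later-month test and, read literally, moves forward to 10 March 2005 unless an end date before enrollment is recorded.

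**Count of possible dates (assumed patient, literal reading).** Diagnosed 15 June 2005, first switch 10 September 2016, events 2006 to 2022.

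- Year-only: 17 possible years. Only 2016 has a rule, so 17 − 1 = 16 are reset to diagnosis. Without a switch, 0 of 17 are.
- Month and year: 17 × 12 = 204 possible months. July to December gives 6 × 17 = 102, less September 2016, so 101 are reset through the gap. June gives a further 17 through the month test. Total reset: 101 + 17 = 118. Of the rest, January to May (5 × 17 = 85) keep their month and 1 goes to the switch date: 118 + 85 + 1 = 204.

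These count possible dates; they do not estimate how often incomplete dates occur.

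**After the change proposed below.** For the second patient, 0 of 17 years and 0 of 204 months are reset to diagnosis. In the first example, 2019 becomes 1 January 2019, May 2019 becomes 1 May, March 2019 becomes 1 March, and May 2003 becomes 31 May 2003.

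**The case against.** The best defense is that the absence of a switch was meant as no switch in that year or month. The year-only gap then closes, and so does the month-year gap apart from the calendar-month fault. The catch-all would still have a job, since a date with a month or day but no year matches no other block. This is a natural reading and may be what the authors intended. But the SAP does not say it, and under it March 2019 is still reset unless year and month are also compared together. Two programmers following the same text could date one FACE about 14 years apart.

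The second objection is exposure. Most FACEs are hard events such as infarction, hospitalization, procedures or dialysis. The form has a field for the event date, sources include national medical records, and FACEs are adjudicated (SAP 13.1). Few onset dates may be incomplete. That stands, and it limits the importance of the point. The protocol's expectation of missing data (Limitations) is about clinical data in general, not event dates. Still, SAP 6.1 provides for such dates, so its rule should work.

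A reader might go further and infer that the primary hazard ratio is biased for or against migalastat. The documents do not support that. The number of partial FACE dates is unknown, and the three routes under the concern push in different directions: one adds an untreated event, one removes a migalastat event, one adds a migalastat event. With few events any single change moves a hazard ratio, which reflects sparse data rather than this rule. Nor is every partly dated FACE of a switcher reset, as the February row shows.

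**Conclusion.** The point holds. Read literally, SAP 6.1 gives an onset that contradicts the recorded year for year-only dates after the enrollment year, and for month-year dates in a later calendar month, whenever the first switch fell in another period. Under a narrower reading of the catch-all, the year-only dates have no rule. Only an unstated reading closes the gap, and it leaves the calendar-month fault, which also reaches never-switchers.

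Each affected date can be wrong by many years (13.8 to 14.8 in the example). The effect on the results is of unknown size and direction. For a patient whose only change is a first treatment start, the gap applies only if that start counts as a switch. The SAP is inconsistent here: 5.1 and 5.2.1 use the word that way, while 8.2 and 11.2 list start and switch separately.

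This should be corrected before onset dates are derived, as wording that is wrong as written. It is not evidence that the primary comparison is compromised.

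**What to change.** In SAP 6.1, SAEs and FACEs:

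1. Make the second sub-rule in each block an explicit otherwise: if the first switch is not in that year, use 1 January; if not in that month, use the first of the month. This extends the default already given to non-switchers.
2. Compare year and month together throughout the month-year block.
3. State that an imputed onset, including one counted back from the end date, must stay within the recorded year or month and must not fall after the end date, death or last contact.
4. Restrict the catch-all to dates with no recorded year. Deleting it would leave those dates without a rule.
5. State whether a first treatment start counts as a switch.

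Optional: tabulate partial and missing FACE dates by treatment group, as 6.1 already does for therapy dates, and add one sensitivity analysis at the earliest and latest dates the record allows.

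The cost is a few lines of SAP text and derivation code; no FACE is dropped. One limitation remains. Events in the switch period are still anchored to the switch date, inside the 30 days that SAP 13.1.1 credits to the prior therapy. In simulations with assumed diagnoses in 2001 to 2015, first switches from 2016 and events spread evenly from switch to end of follow-up, 7% to 18% of year-only post-switch FACEs were anchored this way although they truly occurred more than 30 days after the switch. The optional sensitivity analysis would show whether this matters.
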